6.3. Lifestyle Restrictions

Patients are encouraged to abstain from alcohol consumption during active cluster periods.

6.4. Screen Failures

Individuals who do not meet the criteria for participation in this study (screen failure) may be considered for rescreen once, with approval from Lilly Medical, for only the following criteria:

- Inclusion Criteria 4
- Exclusion Criteria 7
- Exclusion Criteria 8; patients with inadequate washout may be rescreened following an appropriate washout period.
- Exclusion Criteria 10; patients with inadequate washout may be rescreened following an appropriate washout period.

- Exclusion Criteria 11; patients with unstable mood or anxiety disorders may rescreen once that disorder is appropriately stabilized.
- Exclusion Criteria 12; these screen-fail patients may be considered for rescreen if the following conditions are met:
 - The patient was referred to an appropriate mental health professional and received treatment as necessary.
 - At least 6 months has elapsed since the screen-fail.
 - Are not considered by the investigator to be at significant risk for suicide at time of rescreening.
- Exclusion Criteria 13
- Exclusion Criterion 14(f); patients with uncontrolled high blood pressure may be considered for rescreen once their blood pressure is controlled in the opinion of the investigator and at <160/100; any use of antihypertensive medication and dose must be stable for at least 2 months prior to V2.
- Exclusion Criteria 16(b): If a patient fails eligibility due to a positive UDS, the patient may be considered for rescreen.

7. Treatments

7.1. Treatments Administered

All eligible subjects will receive galcanezumab 300 mg during the treatment phase (SP II). The treatment will be administered as three injections each containing 100 mg/1.0 mL by site personnel, during SPII.

The investigator or his/her designee is responsible for the following:

- explaining the correct use of the investigational agent(s) to the site personnel
- verifying that instructions are followed properly
- maintaining accurate records of investigational product dispensing and collection
- returning all unused medication to Lilly or its designee at the end of the study

Note: In some cases, sites may destroy the material if, during the investigator site selection, the evaluator has verified and documented that the site has appropriate facilities and written procedures to dispose clinical trial materials.

Possible injection sites include the abdomen, thigh, and upper arm. Buttocks may also be used, if more appropriate for SC injection than the other sites.

Patients will be instructed to contact the investigator as soon as possible if he or she has a complaint or problem with the investigational product so that the situation can be assessed.

7.1.1. Packaging and Labelling

Galcanezumab for injection, 100 mg/1.0 mL, will be supplied by the sponsor as disposable manual prefilled syringes (during SP II) in accordance with Current Good Manufacturing Practice (cGMP).

Packaging, Preparation, Labeling, and Storage

Galcanezumab solution for injection will be supplied by the sponsor or its designee in accordance with cGMP. Galcanezumab will be supplied as an injectable solution in 1-mL, single-dose, disposable manual syringes. Each syringe of galcanezumab will be designed to deliver 100 mg of galcanezumab. The disposable manual prefilled syringes of galcanezumab for injection, 100 mg/1.0 mL should be stored in the refrigerator (2° C to 8° C). The disposable manual prefilled syringes should be removed from the refrigerated storage and allowed to equilibrate to room temperature for approximately 30 minutes before administration.

Administration of Galcanezumab Using Disposable Manual Prefilled Syringe

Injections will be administered by the clinical staff. A dose will consist of three 1-mL disposable manual prefilled syringes, with each syringe containing 100 mg of galcanezumab, for a total of 300 mg galcanezumab.

7.1.2. Medical Devices

The manufactured medical device provided for use in this study is a disposable manual prefilled syringe.

7.2. Method of Treatment Assignment

All patients will receive the same treatment: galcanezumab 300 mg.

7.2.1. Selection and Timing of Doses

Investigational product (galcanezumab) will be administered as 3 SC injections of not more than once monthly during SP II at the discretion of the investigator. Less than 28 days between doses is a protocol violation.

Investigational product injections should only be administered after all other study procedures are completed for the given visit.

7.3. Blinding

This is an open-label study.

7.4. Dosage Modification

Not applicable.

7.5. Preparation/Handling/Storage/Accountability

Please refer to Section [7.1.1](#).

7.6. Treatment Compliance

To ensure treatment compliance, investigational product will be administered by site personnel. To document treatment administration each injection must be documented in the electronic case report form (eCRF) and follow the Schedule of Activities ([Table 2.1](#)).

7.7. Concomitant Therapy

The list of allowed/not allowed medications and procedures is provided separately in the Protocol Operations Manual. Patients should be instructed to consult with the investigator or study coordinator at the site before taking any new prescribed medications, over-the-counter (OTC) medications, or supplements. If the need for other concomitant medication arises, inclusion or continuation of the patient in the study may be at the discretion of the investigator after consultation with Lilly CRP/CRS or delegate.

7.8. Treatment After the End of the Study

7.8.1. Study Extensions

Not applicable.

7.8.2. Continued Access

Not applicable.

7.8.3. Special Treatment Considerations

Not applicable.

7.8.4. Patient Follow-Up in Pragmatic Trials

Not applicable.

8. Discontinuation Criteria

8.1. Discontinuation from Study Treatment

All patients are free to withdraw from participation in this study at any time and for whatever reason, specified or unspecified, and without prejudice.

Patients who discontinue early from the study should complete study procedures listed in Event List F in the Schedule of Activities.

8.1.1. *Temporary Discontinuation from Study Treatment*

This protocol allows for temporary interruption of treatment, based on clinical symptoms of efficacy and response as judged by the investigator (Section 5.1). Dosing in this scenario may be re-initiated at the study investigator's discretion. If dosing is temporarily interrupted due to a potential safety concern, dosing may be re-initiated at the study investigator's discretion following a discussion and agreement between the study investigator and Lilly Medical that re-initiation of dosing is appropriate.

8.1.2. *Discontinuation of Inadvertently Enrolled*

If the sponsor or investigator identify a patient who did not meet enrollment criteria and was inadvertently enrolled, a discussion must occur between the sponsor CRP and the investigator to determine if the patient may continue in the study. If both agree it is medically appropriate to continue, the investigator must obtain documented approval from the sponsor CRP to allow the inadvertently enrolled patient to continue in the study with or without treatment with investigational product.

8.2. Discontinuation from the Study

All patients may continue in the study and receive treatment with galcanezumab based on the study investigator's judgment of clinical symptoms and response until the end of the study (described in Section 5.3). In addition, the study investigator should consider study discontinuation for an individual patient for the following:

- Lack of benefit. The study physician should consider whether the patient is deriving benefit from galcanezumab.
- Safety concerns, including evaluation of overall risk-benefit.
- The investigator decides that the patient should be discontinued from the study for another reason.
- Enrollment in any other clinical trial involving an investigational product or enrollment in any other type of medical research judged not to be scientifically or medically compatible with this study.
- Participation in the study needs to be stopped for medical, safety, regulatory, or other reasons consistent with applicable laws, regulations, and good clinical practice (GCP).

- Subject decision. The patient requests to be withdrawn from the study.

Discontinuation of the investigational product for abnormal liver tests should be considered by the investigator when a patient meets 1 of the following conditions after consultation with the Lilly designated medical monitor:

- ALT or AST >8X ULN
- ALT or AST >5X ULN for more than 2 weeks
- ALT or AST >3X ULN and TBL level >2× ULN or prothrombin time >1.5X ULN
- ALT or AST >3X ULN with the appearance of fatigue, nausea, vomiting, right upper-quadrant pain or tenderness, fever, rash, and/or eosinophilia (>5%).

It is also recommended to consider discontinuation in a patient with ALP elevation which meets 1 of the following criteria and is deemed to be of liver origin and drug related:

- ALP >3X ULN
- ALP >2.5X ULN and TBL >2X ULN
- ALP >2.5X ULN with the appearance of fatigue, nausea, vomiting, right upper quadrant pain or tenderness, fever, rash, and/or eosinophilia (>5%)

Patients who discontinue from the study early will have end-of-therapy procedures performed as shown in Event List F in the Schedule of Activities ([Table 2.1](#)).

8.3. Lost to Follow-Up

A patient will be considered lost to follow-up if he or she fails to return for scheduled visits and is unable to be contacted by the study site. Site personnel are expected to make diligent attempts to contact patients who fail to return for a scheduled visit or were otherwise unable to be followed up by the site. Diligent attempts will be defined in the Protocol Operations Manual.

9. Study Assessments and Procedures

Section 2 lists the Visit Flow Diagram and Schedule of Activities, with the study procedures and their timing.

Appendix 2 lists the laboratory tests that will be performed for this study.

Appendix 3 lists the hepatic monitoring tests for treatment-emergent abnormalities for this study.

Unless otherwise stated in the subsections below, all samples collected for specified laboratory tests will be destroyed within 60 days of receipt of confirmed test results. Certain samples may be retained for a longer period, if necessary, to comply with applicable laws, regulations, or laboratory certification standards.

9.1. Efficacy Assessments

The Patient Global Impression of Improvement (PGI-I) requests patients to mark the box that best describes your cluster headache condition since you started taking this medicine. The options in the displayed boxes are represented on a seven-point scale, with 1=very much better and 7=very much worse (Guy 1976).

9.1.1. Appropriateness of Assessments

All efficacy and safety assessments have been well documented and are generally regarded as reliable, accurate, and relevant in this patient population.

9.2. Adverse Events

Investigators are responsible for monitoring the safety of patients who have entered this study and for alerting Lilly or its designee to any event that seems unusual, even if this event may be considered an unanticipated benefit to the patient.

The investigator is responsible for the appropriate medical care of patients during the study.

Investigators must document their review of each laboratory safety report.

The investigator remains responsible for following, through an appropriate health care option, AEs that are serious or otherwise medically important, considered related to the investigational product or the study, or that caused the patient to discontinue the investigational product before completing the study. The patient should be followed until the event resolves, stabilizes with appropriate diagnostic evaluation, or is reasonably explained. The frequency of follow-up evaluations of the AE is left to the discretion of the investigator.

Lack of drug effect is not an AE in clinical studies, because the purpose of the clinical study is to establish treatment effect.

After the informed consent form (ICF) is signed, study site personnel will record via eCRF the occurrence and nature of each patient's pre-existing conditions, including clinically significant signs and symptoms of the disease under treatment in the study. In addition, site personnel will record any change in the condition(s) and any new conditions as AEs. Investigators should

record their assessment of the potential relatedness of each AE to protocol procedure, investigational product, via eCRF.

The investigator will interpret and document whether or not an AE has a reasonable possibility of being related to investigational product, study device, or a study procedure, taking into account the disease, concomitant treatment or pathologies.

A “reasonable possibility” means that there is a cause and effect relationship between the investigational product, study device and/or study procedure and the AE.

The investigator answers yes/no when making this assessment.

Planned surgeries and nonsurgical interventions should not be reported as AEs unless the underlying medical condition has worsened during the course of the study.

If a patient’s investigational product is discontinued as a result of an AE, study site personnel must report this to Lilly or its designee via eCRF clarifying if possible, the circumstances leading to discontinuations of treatment.

9.2.1. Serious Adverse Events

An SAE is any AE from this study that results in 1 of the following outcomes:

- death
- initial or prolonged inpatient hospitalization
- a life-threatening experience (that is, immediate risk of dying)
- persistent or significant disability/incapacity
- congenital anomaly/birth defect
- considered significant by the investigator for any other reason: important medical events that may not result in death, be life-threatening, or require hospitalization may be considered serious, based upon appropriate medical judgment.
- when a condition related to the disposable manual prefilled syringe necessitates medical or surgical intervention to preclude either permanent impairment of a body function or permanent damage to a body structure, the serious outcome of “required intervention” will be assigned.

Although all AEs occurring after signing the ICF are recorded in the eCRF, SAE reporting begins after the patient has signed the ICF and has received investigational product. However, if an SAE occurs after signing the ICF, but prior to receiving investigational product, it needs to be reported ONLY if it is considered reasonably possibly related to study procedure.

Study site personnel must alert Lilly or its designee of any SAE within 24 hours of investigator awareness of the event via a sponsor-approved method. If alerts are issued via telephone, they are to be immediately followed with official notification on study-specific SAE forms. This 24-hour notification requirement refers to the initial SAE information and all follow-up SAE information.

Pregnancy (during maternal or paternal exposure to investigational product) does not meet the definition of an AE. However, to fulfill regulatory requirements any pregnancy should be reported following the SAE process to collect data on the outcome for both mother and fetus. Pregnancy cases should be reported up to 5 months after last investigational product administration.

Investigators are not obligated to actively seek AEs or SAEs in subjects once they have discontinued and/or completed the study (the patient summary eCRF has been completed). However, if the investigator learns of any SAE, including a death, at any time after a subject has been discharged from the study, and he/she considers the event reasonably possibly related to the study treatment or study participation, the investigator must promptly notify Lilly.

9.2.1.1. Suspected Unexpected Serious Adverse Reactions

Suspected unexpected serious adverse reactions (SUSARs) are serious events that are not listed in the IB and that the investigator identifies as related to investigational product or procedure. United States 21 CFR 312.32 and European Commission Clinical Trial Directive 2001/20/EC (United States Government Publishing Office [WWW]; European Commission [WWW]) and the associated detailed guidances or national regulatory requirements in participating countries require the reporting of SUSARs. Lilly has procedures that will be followed for the recording and expedited reporting of SUSARs that are consistent with global regulations and the associated detailed guidances.

9.2.1.2. Adverse Event Monitoring with the Columbia-Suicide Severity Rating Scale, Self-Harm Supplement Form, and Self-Harm Follow-up Form

The C-SSRS and SHSF will be administered to assess and evaluate patients for suicide-related events (behavior and/or ideation) at every scheduled and unscheduled office visit as specified in the Schedule of Activities (Table 2.1). Before administering the C-SSRS (Posner et al. 2011), study site personnel will question the patient about any change in the pre-existing condition(s) and the occurrence and nature of any AEs. Nonserious AEs obtained through the questionnaire are recorded and analyzed separately. Only *serious* AEs and AEs leading to discontinuation elicited through the C-SSRS are to be recorded as AEs via eCRF. Serious adverse events must be reported to Lilly or its designee within 24 hours as SAEs. The SHSF captures the number of discrete events of suicidal behavior, possible suicidal behavior, or nonsuicidal self-injurious behavior recorded in the C-SSRS and must be completed at every visit. Additionally, the SHFU will be completed at any visit, including screening/baseline visits, when a suicidal or nonsuicidal self-injurious behavior is identified. At any time during the study, if a patient is considered to be at significant risk for suicide by the investigator, prompt referral of the patient to a mental health professional should be considered.

9.2.2. Complaint Handling

Lilly collects product complaints on investigational products and drug delivery systems used in clinical studies in order to ensure the safety of study participants, monitor quality, and to facilitate process and product improvements.

Clinical staff must report a product complaint to the sponsor if a product quality issue is noted. Timeline expectations and instructions on how to report a product quality complaint are located on the provided study specific product complaint form. For an SAE attributable to a product quality issue or defect, the complaint must be reported within the same timeframe as the SAE.

9.3. Treatment of Overdose

Data not available.

9.4. Safety

9.4.1. *Electrocardiograms*

For each patient, 12-lead digital ECGs will be collected according to the Schedule of Activities (Table 2.1) as single ECGs for overread. Patients must be supine for approximately 5 to 10 minutes before ECG collection and remain supine but awake during ECG collection.

Electrocardiograms will be interpreted by a qualified physician (the investigator or qualified designee) at the site as soon after the time of ECG collection as possible, and ideally while the patient is still present, to determine whether the subject meets entry criteria and for immediate subject management, should any clinically relevant findings be identified. Electrocardiograms may be obtained at additional times, when deemed clinically necessary.

Electrocardiograms will have a central overread. The investigator (or qualified designee) must document his/her review of the ECG printed at the time of evaluation, the final overread ECG report issued by the central ECG laboratory, and any alert reports.

9.4.2. *Vital Signs*

Blood pressure and pulse will be collected in triplicate according to the Schedule of Activities (Table 2.1) and at unscheduled office visits. All sites will be provided with an automated blood pressure machine with several cuff sizes. The following guidelines will be used by investigative sites when measuring vital signs:

- Blood pressure and pulse must be measured before any blood draws.
- Blood pressure will be measured in sitting position with both feet resting on the floor after the patient has rested for at least 5 minutes.
- Blood pressure will be measured with a cuff that is appropriate to the size of the patient.
- Use the same arm for blood pressure collection throughout the study.
- Arm with cuff must be supported at approximately the heart level.
- Three sitting blood pressures and pulse measurements will be collected at approximately 30 to 60 second intervals.

9.4.3. *Laboratory Tests*

For each patient, laboratory tests detailed in ([Appendix 2](#)) should be conducted according to the Schedule of Activities [Table 2.1](#)).

Any clinically significant findings from laboratory tests that result in a diagnosis and that occur after the patient receives the first dose of investigational product should be reported to Lilly or its designee as an AE via eCRF.

9.4.4. *Safety Monitoring*

Lilly will periodically review evolving aggregate safety data within the study by appropriate methods.

Lilly will review SAEs within time frames mandated by company procedures. The Lilly CRP/clinical research scientist (CRS) will, as is appropriate, consult with the functionally independent Global Patient Safety therapeutic area physician or clinical scientist, and periodically review:

- trends in safety data
- laboratory analytes
- AEs including monitoring of injection site reactions, allergic reactions, and infections

If a study patient/subject experiences elevated ALT $\geq 3 \times$ ULN, ALP $\geq 2 \times$ ULN or elevated TBL $\geq 2 \times$ ULN, clinical and laboratory monitoring should be initiated by the investigator. Details for hepatic monitoring depend upon the severity and persistence of observed laboratory test abnormalities. To ensure patient/subject safety and comply with regulatory guidance, the investigator is to consult with the Lilly designated medical monitor regarding collection of specific recommended clinical information and follow-up laboratory tests ([Appendix 3](#)).

9.4.5. *Samples for Immunogenicity Research*

Where local regulations and ethical review boards (ERB) allow, blood samples for immunogenicity testing will be collected to determine antibody production against galcanezumab as specified in the Schedule of Activities ([Table 2.1](#)). Immunogenicity will be assessed by a validated assay designed to detect anti-drug antibody (ADAs) in the presence of the investigational product. Antibodies may be further characterized and/or evaluated for their ability to neutralize the activity of the investigational product.

Anti-drug antibody sampling will be initiated immediately prior to first patient dosing with galcanezumab (baseline). Immunogenicity samples must be collected prior to dose administration if the visit is a dosing visit, and the timing of all samples will be recorded.

Samples will also be drawn in the event of early termination or as needed given any safety concerns judged to potentially immunologically mediated.

Samples

Samples will be drawn at Month 0 (first dose), Month 1, Month 6, and then every 6 months, thereafter; prior to dosing unless dosing is temporarily halted due to a clinical efficacy response. When dosing is temporarily halted due to a clinical efficacy response, an immunogenicity sample is scheduled for 1 month after the last dose of galcanezumab. When dosing is resumed, an immunogenicity sample is drawn prior to dosing (Section 2, Schedule of Activities). Additionally, at study termination samples will be drawn approximately 1 month after the last dose of galcanezumab.

Samples will be retained for a maximum of 15 years after the last patient visit for the study, or for a shorter period if regulations and ERBs impose shorter time limits, at a facility selected by Lilly. The duration allows the sponsor to respond to future regulatory requests related to the investigational product.

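### The hepatic monitoring trigger in Protocol 9.4.4 leaves out AST, although the discontinuation conditions in 8.2 treat ALT and AST alike

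*Protocol*

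**What the plan says.** Protocol 9.4.4 (Safety Monitoring) names three triggers: ALT ≥3× ULN, ALP ≥2× ULN and TBL ≥2× ULN. When one is met, "clinical and laboratory monitoring should be initiated by the investigator". The extent is left open: "Details for hepatic monitoring depend upon the severity and persistence of observed laboratory test abnormalities". The section then adds that "the investigator is to consult with the Lilly designated medical monitor regarding collection of specific recommended clinical information and follow-up laboratory tests", and it points to Appendix 3.

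Protocol 8.2 lists the liver-test conditions under which stopping the drug should be considered, "when a patient meets 1 of the following conditions after consultation with the Lilly designated medical monitor". There are four aminotransferase conditions, and each gives ALT and AST one shared threshold. One is "ALT or AST >5X ULN for more than 2 weeks". Another pairs a rise above 3× ULN with TBL above 2× ULN "or prothrombin time >1.5X ULN". The ALP conditions include "ALP >2.5X ULN and TBL >2X ULN".

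AST is in the routine chemistry panel (Appendix 2) and the hepatic panel (Appendix 3). Prothrombin time is only in Appendix 3.

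**The concern.** For ALT, ALP and TBL, 9.4.4 acts as an early warning for 8.2: its level is at or below the lowest value at which 8.2 could apply. For AST there is no such level, and neither document says why.

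A patient whose AST rises while ALT stays below 3×, ALP below 2× and TBL below 2× ULN therefore gets no specific recommendation for monitoring or consultation until an 8.2 condition is already met. Two of those conditions cannot be established from the routine sample that revealed the rise. One needs evidence of persistence and the other needs a coagulation test. For an ALT rise, 9.4.4 prompts the steps that can supply this evidence; for an AST rise it does not. What is at stake is a possible delay in recognising a condition that the protocol itself regards as a reason to consider stopping treatment.

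**Working it through.** There is no planned figure to reproduce. The check compares 9.4.4 with 8.2 analyte by analyte and then branch by branch.

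**Step 1: trigger level against the lowest 8.2 threshold**

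| Analyte | 9.4.4 level (× ULN) | Lowest 8.2 threshold (× ULN) | Trigger at or below it? |
|---|---|---|---|
| ALT | ≥3 | >3 | yes |
| ALP | ≥2 | >2.5 | yes |
| TBL | ≥2 | >2 | yes |
| AST | none | >3 | no trigger |

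Three of the four chemistry analytes are covered, and AST is not.

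**Step 2: the 8.2 aminotransferase branches.** The third condition is read as aminotransferase above 3× ULN together with either raised TBL or raised prothrombin time, so the four conditions give five branches. The last two columns show whether 9.4.4 would already have fired.

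| Branch | Via ALT | Via AST alone |
|---|---|---|
| 1. >8× | yes | no |
| 2. >5× for more than 2 weeks | yes | no |
| 3a. >3× with TBL >2× | yes | yes, through TBL ≥2× |
| 3b. >3× with prothrombin time >1.5× | yes | no |
| 4. >3× with symptoms or eosinophilia | yes | no |

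- Unprompted via ALT: 0 of 5.
- Unprompted via AST alone: 4 of 5 (branches 1, 2, 3b and 4).
- Branches 1 and 4 can be judged from the sample in hand and the clinical findings, and meeting either brings in the 8.2 consultation directly. The practical gap is branches 2 and 3b, or 2 of 5.
- With AST ≥3× added to 9.4.4, every branch lies at or above a trigger, so 0 of 5 are unprompted.

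**Step 3: when the next routine sample would come.** Table 2.1 schedules chemistry in Event Lists A (screening), D (Month 6 and every 6 months after) and F (first visit after a dose when dosing has stopped). Footnotes d and e add it before a delayed Visit 2 and before re-initiation of dosing.

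Under continuous monthly dosing from Month 0 to Month 12:
- There are 13 dosing visits, with chemistry at Months 6 and 12, so 2 of 13.
- The spacing is 365/2 = 182.5, about 183 days; 183/14 ≈ 13 times the 2-week window in branch 2.
- Doses after the Month 6 visit and before the Month 12 sample fall at Months 7, 8, 9, 10 and 11, so five.

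This schedule is the same for every analyte. It shows why a prompt to retest is useful, but it does not measure the effect of omitting AST.

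**The case against.** The two sections do different jobs and need not list the same analytes. An early screen led by ALT is defensible, because AST can rise from sources other than the liver. Exclusion criterion 15c also names only ALT, TBL and ALP, so the omission may be a sponsor convention.

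Much of the gap is covered elsewhere. An investigator who sees AST above 5× ULN can apply the 8.2 persistence condition only by taking another sample, so 8.2 is itself a partial prompt. Appendix 3 is not limited by analyte and allows follow-up tests for any treatment-emergent hepatic abnormality. Section 9.2 states "Investigators must document their review of each laboratory safety report" and asks for follow-up of medically important or drug-related events. The sponsor reviews laboratory analytes periodically. The 183-day and five-dose figures describe a worst case in which the investigator does nothing, and 9.4.4 fixes no retest interval or prothrombin time even for ALT.

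Most of this stands as a limit on size. It does not remove the point. Criterion 15c governs entry, not on-treatment monitoring, and 8.2 does not follow an ALT-only convention: it limits its ALP conditions to elevations judged to be of liver origin and drug related, but sets no such limit for AST. The general safeguards apply equally to ALT, ALP and TBL, which were still given numeric triggers. The 8.2 consultation is tied to meeting a condition, Appendix 3 is permissive, and 9.2 leaves follow-up frequency to the investigator.

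**Conclusion.** The concern holds, at minor severity. An AST-only rise lacks the early monitoring recommendation and consultation that an equal ALT rise receives. The gap covers four of the five 8.2 branches on paper and two in practice (>5× ULN for more than 2 weeks, and the prothrombin-time branch). AST rises are not ignored; they lack a prompt.

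This rests on the reading of the third 8.2 condition given above and on rises confined to AST. The documents give no AST event rate, so the number of patients cannot be estimated; it is probably small. No endpoint analysis is affected, and SAP 5.16.8 still summarises treatment-emergent high values for each laboratory test.

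**What to change.** In Protocol 9.4.4, replace ALT ≥3× ULN with ALT or AST ≥3× ULN and leave the ALP and TBL triggers as they are. The prompt then comes at or before every 8.2 aminotransferase branch, whichever enzyme is raised. Retest timing and prothrombin time remain matters for the consultation, as they now are for ALT.

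The cost is one line at the next amendment. AST is already in the Appendix 2 panel, so no scheduled test is added. There will be occasional repeat panels and consultations for AST rises not of liver origin; creatine kinase, also in Appendix 2, helps to identify these.
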